# 2.4.5 Rationale for Endpoints

# 2.4.5.1 Biomarker and Expression of Transgene Endpoints

Despite clinical activity of immunotherapies across a range of cancer types, the majority of participants fail to respond while immune mechanisms remain incompletely defined. To maximize the impact of therapy, well-characterized biomarkers are needed. We will correlate biomarkers with pharmacodynamic activity and bioactivity of VB-111, in search of a novel tumor tissue-based assay that may predict efficacy of VB-111, allow for monitoring of response, and identify subclinical immune-driven toxicity.

Changes in the local and systemic immune environment have been observed with VB-111 in preclinical models and clinical trials. Orthotopic U251 tumor microglia and T cell co-cultures in mice 6 hours after VB-111 administration exhibited a significant increase in several cytokines

correlating with overall survival, including IL-1R17 $\alpha$ , IL-1 $\alpha$ , MIP1 $\alpha$ , and TNF $\alpha$  (p<0.05). They also demonstrated decrease in immunosuppressive cytokines, including IL-10, IL-4, IL-3, and IL-5 [53]. A human phase 1 trial revealed variability in cytokine and cytokine receptor levels. IL-6 demonstrated a transient 100-fold increase at 6 hours after dosing, correlating with concurrent fever. Statistically significant small transient increases were also noted in sCD54 (p=0.03) and TNFR-2 (p=0.002) at several time points over 28 days after dosing [45].

In this study, TIL density and TCR clonality will be quantitatively assessed with next generation TCR sequencing [54]. Expansion of TCR clones can be compared in VB-111 neoadjuvant vs placebo followed by postoperative VB-111.

Tumor and peripheral blood gene expression signatures and somatic mutations will be measured by RNA-seq and Exome sequencing. Cell-cycle related gene signatures will be measured by RNA-seq and Nanostring IO360.

Tumor and peripheral blood T cell subsets and activation markers will be assessed with mass cytometry high dimensional analysis to identify immune cell subsets that expand or contract in an unbiased fashion during treatment.

Tumor quantification of PD-1, PD-L1, CD3, CD4, CD8, Iba-1, Ki-67 will be measured by immunohistochemistry of FFPE tissue. Multiplex immunofluorescence will be used to spatially quantitate TIL in the tumor microenvironment.

VB-111 is an anti-angiogenic agent developed by VBL based on an adenovirus vector. It is a nonreplicating E1 deleted, Adenovirus 5, carrying a pro-apoptotic human Fas-chimera (transgene) under the control of a modified murine promoter (PPE-1-3x). The transgene is specifically expressed in angiogenic endothelial cells. In this study, we will explore and validate the presence and expression of viral transgene in the tumor tissue.

# 2.4.5.2 Safety Endpoints

A primary objective of this study is to characterize the safety and tolerability of VB-111 in the preand post- operative settings in surgically resectable recurrent glioblastoma. Safety analysis will be based on toxicities and grades as defined by CTCAE version 5.0 criteria, including serious adverse events (SAEs). The attribution to drug, time-of-onset, duration of the event, resolution, and any concomitant medications administered will be recorded. AEs analyzed include but are not limited to all AEs, SAEs, and fatal AEs.

# 2.4.5.3 Efficacy Endpoints

Primary efficacy endpoint will be T lymphocyte (TIL) density, and the secondary efficacy endpoint PFS6 will be measured using RANO criteria. RANO criteria [55] as assessed by the investigator will be used to determine eligibility, make treatment decisions, and determine progression. KPS [Appendix A] as assessed by the investigator will be used to determine clinical progression. OS will be calculated based on time-to-event outcome.

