# 5.4 Trial Blinding/Masking

Pre-operative treatment will be blinded; therefore, the treating investigator and subject will not know whether VB-111 or placebo is administered. An unblinded pharmacist or designee not involved in other study assessments will prepare the Pre-operative study drug of VB-111/Placebo. Post-operatively, treatment will be unblinded.

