- 19. Adverse events experienced by participants will be collected and recorded from the first dose of study treatment up to the 30-Day Post Drug Visit of the last dose of study medication (+ 7 days depending on when 30-Day Post Drug visit/contact occurs) and all SAEs (related and unrelated to trial treatment) up to 90 days after the last dose of treatment. Afterwards, report only SAEs that are considered related to trial treatment. Adverse events may also occur in screened participants during pre-allocation baseline period as a result of a protocol-specific intervention, including washout or discontinuation of usual therapy, diet, placebo treatment or a procedure.
- 20. For women of child bearing potential, a urine pregnancy test must be performed. If urine pregnancy results cannot be confirmed as negative, a serum pregnancy test will be required.
- 21. PT/INR, PT, PTT are required at screening and PTT will be checked again with pre-surgery labs. Thereafter,

coagulation to be checked when clinically indicated.

- 22. Hematology includes erythrocytes (RBC), hemoglobin, hematocrit, platelets, total WBC plus differential (neutrophils, lymphocytes, monocytes, eosinophils, basophils).
- 23. Serum Chemistry includes albumin, alkaline phosphatase (ALP), bicarbonate (HCO3), BUN, calcium, chloride, creatinine, glucose, magnesium, potassium, SGOT (AST), SGPT (ALT), sodium, total protein, total bilirubin.
- 24. Virology panel includes Hepatitis A Antibody, Hepatitis B Core IgG and M Antibody (Anti-HBC, total), Hepatitis B Surface Antibody (Anti-HBs), Hepatitis B Surface Antigen (HBsAg), Hepatitis C Surface Antibody (anti-HCV), HIV-1/2 Ag/Ab and HTLV-1/2 Ag/Ab. If any hepatitis serology is positive, qualitative PCR for Hepatitis B DNA or Hepatitis C RNA will be obtained and results must be negative for eligibility.
- 25. Imaging: gadolinium-enhanced contrast and non-contrast MRI. Initial imaging should be performed within 14 days prior to enrollment. On-study imaging should be performed every 6 weeks starting from post-surgery treatment Cycle 1 Day 1. The same imaging technique should be used in a participant throughout the trial, if feasible. Local reading (investigator assessment) will be used to determine eligibility and for participant management.
- 26. Response Assessment to be completed per RANO criteria (Section 10).

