# **11. MEASUREMENT OF EFFECT**

Tumor response will be assessed every 6 weeks using contrast and non-contrast brain magnetic resonance imaging (MRI) with assessment based on the RANO criteria [55] until progression is supported by two consecutive time points of tumor growth (local and central blinded independent radiology review). For participants who do not progress or die, PFS will be censored at the last adequate radiologic assessment. Baseline scan for determining progression will be the post-operative scan obtained just prior to initiating post-operative therapy.

Clinicians may repeat response assessment more frequently as clinically indicated.

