11.1.6 Guidelines for Evaluation of Measurable Disease

All measurements should be taken and recorded in metric notation using a ruler or calipers. All baseline evaluations should be performed up to 28 days before the beginning of the treatment.

Conventional MRI is required, CT is not acceptable. The same method of assessment and the same technique should be used to characterize each identified and reported lesion at baseline and during follow-up. These techniques should be performed with contiguous cuts of 10mm or less in slice thickness. The MRIs will be evaluated both locally and centrally by a core lab.

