## 11.5 Radiology Review

The review of the baseline neuroimaging will be performed at DFCIto ensure the participants meet the inclusion criterial before the randomization. The review of on-study neuroimaging will be performed retrospectively at DFCI.

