## **3.7.4 Unblinding**

The day after a participant's scheduled surgery, the Multi-Center Coordinating Center will email the participating site team to confirm participant's surgery. Once surgery has been confirmed, the Multi-Center Coordinating Center specialist will obtain the participant's randomization assignment from the 19-792 Unblinded Contact (or back-up) and will email the unblinded treatment assignment to the Participating Site Team. If patient is in Group C, the Participating Site Team will need to provide patient's SOC treatment plan as soon as possible. Once participant's adjuvant therapy is known (Group A or B)/confirmed (Group C), the Multi-Center Coordinating Center specialist will Register the participant centrally to his/her Step 2 Adjuvant Therapy and will email the Participating Site Team to confirm Step 2 Registration. **NOTE: Adjuvant treatment may not begin without** 

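### The documents disagree on whose RANO reading defines PFS6, and one candidate reader knows the treatment group

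*Combined protocol and SAP*

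**What the plan says.** Section 2.4.5.3 makes PFS6 by RANO the secondary efficacy endpoint. It then says that RANO "as assessed by the investigator will be used to determine eligibility, make treatment decisions, and determine progression", and that KPS "as assessed by the investigator will be used to determine clinical progression".

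The investigator knows the group by then. Section 5.4: "Post-operatively, treatment will be unblinded". Under section 3.7.4 of Appendix B the coordinating centre, having confirmed surgery, "will email the unblinded treatment assignment to the Participating Site Team". PFS6 is counted from surgery (13.1.1) and progression is judged against a post-operative scan (section 11), so the on-treatment calls that feed PFS6 are made with the group known.

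Other sections point elsewhere:

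- Section 11 ties RANO progression to "local and central blinded independent radiology review" and gives the PFS censoring rule in the next sentence.
- Section 11.1.6: "The MRIs will be evaluated both locally and centrally by a core lab".
- Section 11.5: "The review of on-study neuroimaging will be performed retrospectively at DFCI". Blinding is not mentioned there.
- Section 10, footnote 25: "Local reading (investigator assessment) will be used to determine eligibility and for participant management". No endpoint role is given.
- Section 13.1.1 defines PFS6 by RANO and names no reader. Section 13.4 lists A vs C, B vs C and A+B vs C, tested exactly with Bonferroni adjustment at one-sided 5%. It names no reader and gives no rule for disagreement between reads.

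**The concern.** All three PFS6 comparisons set VB-111 against an open-label control. RANO progression in section 11.2.4 includes items of judgement: whether a T2/FLAIR increase is significant and not a treatment effect, and whether clinical deterioration is clear and due to tumor. A reader who knows the group can lean on such calls without intending to, and a difference in reading between groups would look like a treatment effect. An unnamed source also leaves the choice between two sets of progression dates open until both have been seen.

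**Working it through.** **Sections side by side**

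| Place | Reader for progression |
|---|---|
| 2.4.5.3 | Investigator |
| 11 | Local and blinded central |
| 11.1.6 | Local and a core lab |
| 11.5 | Retrospective, lead centre, blinding not stated |
| 10, footnote 25 | Local read for eligibility and management only |
| 13.1.1, 13.4 | Not stated |

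No two of these fully settle the question, and the statistical sections, which should, are silent.

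**Illustration of size**

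The plan states no power or error figure for PFS6, so there is nothing to reproduce first.

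Inputs from the documents: 15 per group (13.3), so A+B = 30 and C = 15; three comparisons at one-sided 5% with Bonferroni (13.4), so 0.05/3 = 0.0167 each; historical PFS6 of 10% (13.4).

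Assumptions that are not in the documents:

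- The exact binomial test of two groups is taken as a one-sided Fisher test.
- True PFS6, p, is the same in every group, at 10% or 20%.
- A share m of true progressions by 6 months goes uncalled in A+B and none in C.
- PFS6 uses the ITT set (13.2), which may exceed 15 per group because unevaluable participants are replaced; 15 is used here.

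Apparent PFS6 in A+B is p + (1 − p)m. For p = 0.20 and m = 0.10 this is 0.20 + 0.80 × 0.10 = 0.28.

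The rejection probability is the sum, over all x of 30 and y of 15, of Bin(x; 30, apparent p) × Bin(y; 15, p), taken where the hypergeometric tail P(X ≥ x, given total x + y) is at most alpha.

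| True PFS6 | m | Apparent A+B | Rejects at 0.0167 | Rejects at 0.05 |
|---|---|---|---|---|
| 20% | 0 | 0.20 | 0.5% | 2.3% |
| 20% | 10% | 0.28 | 2.4% | 8.2% |
| 20% | 20% | 0.36 | 7.3% | 19.4% |
| 20% | 30% | 0.44 | 17.5% | 35.5% |
| 10% | 0 | 0.10 | 0.04% | 0.6% |
| 10% | 10% | 0.19 | 2.1% | 8.6% |
| 10% | 20% | 0.28 | 11.6% | 28.4% |
| 10% | 30% | 0.37 | 28.8% | 53.2% |

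The 0.0167 column is the one that matches the plan. For scale, one changed call moves PFS6 by 1/15 = 6.7 points in a single group and by 1/30 = 3.3 points in A+B.

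**The case against.** A reader might infer that the plan settles on the unblinded investigator. It does not. Section 2.4.5.3 is background rationale; section 11, which puts PFS into operation, names both reads; and footnote 25 gives the local read no endpoint role. This stands: the defect is a conflict between sections, not a decision for the wrong reader.

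A reader might also infer that the pseudoprogression text gives VB-111 a more lenient rule. The documents do not support that. Section 11.4 is exploratory, while PFS6 uses standard RANO. Confirmed progression is back-dated to its first date, so waiting for confirmation does not in itself delay the event. The section is written for participants on the study generally, and section 5.1 has progression in Group C determined as in A and B. Knowledge of the group could still sway marginal calls, but neither direction nor size follows from the text.

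The illustration is also open to challenge. The misread rates have no source, and the model needs progressions to stay uncalled to 6 months despite MRI every 6 weeks. At the Bonferroni level a 10% misread leaves the error below 5%. PFS6 is a secondary endpoint without a power statement, and section 1.3 frames its objective as estimation. These points limit the weight of the concern. They do not supply the missing reader.

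**Conclusion.** The point holds as an inconsistency about the source of PFS6, with a risk of bias if section 2.4.5.3 is the text followed. Under the stated assumptions, false-positive rates for A+B vs C at 0.0167 rise from 0.5% to between 2.4% and 17.5% (true PFS6 20%), or from 0.04% to between 2.1% and 28.8% (true PFS6 10%), as 10% to 30% of progressions go uncalled in A+B only. These figures show sensitivity; they do not predict what will happen. TIL density, measured on tissue taken while treatment is blinded, and OS are not touched. It should be corrected, but it does not threaten the primary analysis.

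**What to change.** - In 13.1.1, define PFS6 and PFS by the planned central RANO read, blinded to group and to the local read, with death and documented clinical deterioration also counting as events.
- State that the central read prevails for the endpoint when the two disagree.
- Keep the investigator read for eligibility and participant management, as footnote 25 has it, and as a sensitivity analysis for PFS6.
- Align 2.4.5.3 with this.
- Reconcile 11.1.6 and 11.5 with section 11, so that it is clear who performs the retrospective review and that it is blinded.

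The cost is wording. The central read is already planned, and no sample size, alpha or treatment decision changes. There are three downsides. The endpoint waits for the retrospective read. Local and central dates will sometimes differ. Progression by clinical deterioration stays with unblinded investigators, so bias is reduced and not removed.

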# **3. PARTICIPANT SELECTION**

Screening evaluations are detailed in Study Calendar (Section 10). The participant must be thoroughly informed about all aspects of the study, including the study visit schedule and required evaluations and all regulatory requirements of informed consent. The signed informed consent must be obtained from the participant prior to enrollment. All assessments are to occur within 28 days of registration except where otherwise noted.

Following registration, any additional laboratory assessments prior to start of treatment will not be used to reconfirm eligibility. Please refer to Section 6.0 Dose Delay for toxicity management between registration and start of study treatment.

#### 3.1 Inclusion Criteria

- **3.1.1** Histologically confirmed World Health Organization Grade IV malignant glioma (glioblastoma or gliosarcoma).
- **3.1.2** First or second progression of glioblastoma/gliosarcoma (according to RANO criteria) following standard of care treatment upon initial diagnosis with radiation.
- **3.1.3** Measurable disease by RANO criteria at progression.
- **3.1.4** The maximal tumor volume at baseline meets the following criteria as determined by a local site investigator or surgeon: Longest diameter  $\leq 4$ CM.
- **3.1.5** Surgically resectable disease at progression.
- **3.1.6** An interval of the following durations prior to randomization:
  - At least 28 days from prior surgical resection, or 7 days from stereotactic biopsy
  - At least 12 weeks from prior radiotherapy, unless there is unequivocal histologic confirmation of tumor progression
  - At least 23 days from prior chemotherapy
  - At least 42 days from nitrosureas
  - At least 42 days from other anti-tumor therapies (including vaccines)
  - At least 28 days from immune checkpoint blockade
  - At least 28 days or 5 half-lives from any investigational agent, whichever is shorter.

NOTE: no wash-out period required from TTF.

- **3.1.7** All clinically significant toxic effects of prior therapy must have recovered to grade 0 or 1 or pre-treatment baseline. Allowable exceptions are: alopecia, lymphopenia, and any laboratory value listed elsewhere in the inclusion criteria (provided it meets that criterion's requirements). Please contact the Overall Principal Investigator, [name], for questions regarding exceptions to this criterion.
- **3.1.8** Corticosteroid use at or less than dexamethasone 2mg daily. Participants should be on a stable or decreasing dose for at least 7 days prior to randomization.
- **3.1.9** Age  $\geq$  18 years on day of signing informed consent

- **3.1.10** KPS  $\geq$  70% (see Appendix A)
- **3.1.11** Adequate bone marrow, liver, and renal function according to the following criteria:
  - Absolute neutrophil count  $\geq$  1,500 cells/mL ~ 1.5 K/µL
  - Platelets  $\geq 100,000 \text{ cells/mL} \sim 100 \text{ K/}\mu\text{L}$
  - Total bilirubin  $\leq$  1.5 X institutional ULN **OR** Direct bilirubin  $\leq$  institutional ULN for subjects with total bilirubin levels > 1.5 institutional ULN
  - Aspartate aminotransferase (AST)  $\leq 2.0 \text{ x ULN}$
  - Serum creatinine level ≤ ULN or creatinine clearance ≥ 50 mL/min for participants with creatinine levels above normal limits (calculated by the Cockcroft-Gault formula)
- **3.1.12** Ability to understand and willingness to sign a written informed consent document
- **3.1.13** Availability of 10 unstained formalin-fixed paraffin-embedded slides.
- **3.1.14** Patients must be able to tolerate MRIs.
- 3.1.15 MRI within 14 days prior to registration.

**NOTE:** Due to the fact that the screening MRI will not be used for response purpose, participants may be registered if screening MRI is > 14 days of registration if prospective approval is received from Overall PI, [name] (for prospectively approved circumstances an eligibility exception will not need to be filed).

**3.1.16** Women of childbearing potential must have a negative serum beta-human chorionic gonadotropin urine or serum pregnancy test within 72 hours prior to registration. If the urine test is positive or cannot be confirmed as negative, a serum pregnancy test will be required.

**NOTE:** Women are considered postmenopausal and not of child bearing potential if they have had 12 months of natural (spontaneous) amenorrhea with an appropriate clinical profile (e.g., age appropriate, history of vasomotor symptoms) or six months of spontaneous amenorrhea with serum FSH levels > 40 mIU/mL and estradiol < 20 pg/mL or have had surgical bilateral oophorectomy (with or without hysterectomy) at least six weeks ago. In the case of oophorectomy alone, only when the reproductive status of the woman has been confirmed by follow up hormone level assessment is she considered not of child bearing potential.

**3.1.17** Males and females of childbearing potential must utilize a standard contraception method throughout the trial and up to 120 days after the last dose of treatment on study.

**NOTE**: Women of childbearing potential and men with female spouses of childbearing potential must agree to use two methods of reliable contraception simultaneously or to practice complete abstinence from heterosexual contact prior to study entry, while receiving treatment, and for 4 months after undergoing treatment. One method must include a highly effective method such as an intrauterine device, hormonal (birth control pills, injections or implants), tubal ligation or partner's vasectomy. The other method can be an additional hormonal therapy or barrier method such as a male condom, diaphragm or cervical cap. Should a woman become pregnant or suspect she is pregnant while she or her partner is participating in the study, she should inform her treating physician immediately.

#### 3.2 Exclusion Criteria

- **3.2.1** Current or planned participation in a study of an investigational agent or using an investigational device.
- **3.2.2** Has tumor primarily localized to the brainstem or spinal cord
- **3.2.3** Has presence of diffuse leptomeningeal disease or extracranial disease.
- **3.2.4** Surgical procedure (including open biopsy, surgical resection, wound revision, or any other major surgery involving entry into a body cavity) or significant traumatic injury within 28 days prior to first study treatment
- **3.2.5** Minor surgical procedure (e.g. stereotactic biopsy or shunt placement) within 7 days of first study treatment, placement of vascular access within 2 days of first study treatment
- **3.2.6** Expected to have surgery other than the neurosurgical procedure intended for the GBM lesion during study treatment period
- **3.2.7** Prior stereotactic radiotherapy (Note: those who have had biopsy proven tumor recurrence at a site of SRS treatment should be considered eligible if approved by the study central Investigator)
- **3.2.8** Prior anti-angiogenic therapy including VEGF sequestering agents (i.e. bevacizumab, aflibercept, regorafenib, etc.) or VEGFR inhibitors (cedirinib, pazopanib, sunitinib, sorafenib, etc.)
- **3.2.9** Prior administration of the study drug VB-111
- **3.2.10** Concomitant medication that may interfere with study results (e.g. immunosuppressive agents other than inhaled, topical or intra-articular steroids or a stable or decreasing dose of oral corticosteroids of up to <2 mg/day dexamethasone equivalent)
- **3.2.11** Known active second malignancy. Exceptions include non-melanoma skin cancers, non-metastatic prostate cancer, in situ cervical cancer, and ductal or lobular carcinoma in situ of the breast. Participants are not considered to have currently active malignancy if they have completed anticancer therapy and have been disease free for greater than 2 years prior to screening
- **3.2.12** Uncontrolled intercurrent illness including but not limited to ongoing or active infection, symptomatic congestive heart failure, unstable angina pectoris, cardiac arrhythmia, or psychiatric illness/social situations that would limit compliance with study requirements
- **3.2.13** History of stroke or transient ischemic attack within 6 months prior to randomization
- 3.2.14 Evidence of CNS hemorrhage CTCAE grade 2 or above on screening MRI
- **3.2.15** Active cardiac disease within 6 months prior to randomization (i.e. acute coronary syndrome, unstable angina, New York Heart Association grade II or greater congestive heart failure, or serious cardiac arrhythmia uncontrolled by medication or potentially interfering with protocol treatment)

- **3.2.16** Significant vascular disease within 6 months prior to randomization (e.g. aortic aneurysm requiring surgical repair, peripheral arterial thrombosis, symptomatic peripheral vascular disease)
- 3.2.17 History of venous thromboembolism CTCAE version 5.0 grade 3 or greater
- 3.2.18 Known proliferative and/or vascular retinopathy
- **3.2.19** Inadequately controlled hypertension (defined as systolic blood pressure > 150mmHg and/or diastolic blood pressure > 100mmHg) within 1 week of randomization
- **3.2.20** History of pulmonary hemorrhage/hemoptysis  $\geq$  grade 2 (defined as  $\geq$  2.5 mL bright red blood per episode) within 6 months of randomization.
- **3.2.21** History of active gastrointestinal bleeding within 6 months prior to randomization.
- **3.2.22** History or evidence of inherited bleeding diathesis or significant coagulopathy at risk of bleeding (i.e. in the absence of therapeutic anticoagulation)
- **3.2.23** Current or recent (within 10 days of study randomization) use of aspirin > 325mg/day, clopidogrel > 75mg/day or equivalent. Therapeutic or prophylactic use of anticoagulants is allowed
- **3.2.24** Known liver disease (alcoholic, drug/toxin induced, genetic or autoimmune)
- **3.2.25** History of gastrointestinal perforation or abscess
- **3.2.26** Positive testing to any of the following viruses: HIV, HBV, HCV within the last 6 months. Exceptions include participants with serology positive for HBV indicating past exposure but without evidence of active infection (e.g. negative PCR)
- **3.2.27** History of intracranial abscess within 6 months prior to randomization
- 3.2.28 Serious non-healing wound, active ulcer, or untreated bone fracture
- **3.2.29** Pregnant or breastfeeding participants

